5.2.1.3 Definition of Dose-Limiting Toxicities

All toxicities will be graded using the National Cancer Institute (NCI) CTCAE v5.0 (Appendix 2; Section 13.2). Dose-limiting toxicity (DLT) assessment will be based on events occurring during the DLT assessment period, which is defined as course 1. Dose-limiting toxicities include all adverse experiences that are clearly not related to disease progression or intercurrent illness if judged by the investigator to be possibly, probably, or definitely related to study treatments that meet or exceed the following severity criteria:

- Toxicities associated with pembrolizumab representing autoimmune phenomenon have been extensively characterized, and may be exacerbated by combination treatment with IL-2. Treatment associated AE's that represent immune mediated pathology are codified in [Section 5.2.1.4](#), Table 4. For patients at Dose Level 1, all AE's resulting in Guideline recommendation for Treatment Discontinuation will also constitute a DLT.
- A delay in the scheduled administration of either component of therapy of > 21 days for pembrolizumab or SQ or IV bolus IL-2.
- Bolus IV dosing of IL-2 (Dose Level 2 and 3), especially at Dose Level 3, is known to be associated with acute severe toxicities. Doses are administered to patient tolerance according to established treatment guidelines (Appendix 4, Section 13.4). Toxicities associated with IL-2 administration will be initially managed according to the IL-2 Toxicity Management Guidelines (Appendix 4, Section 13.4). Toxicities that fail to stabilize within 48 hours of the last IL-2 dose or that fail to show improvement within 72 hours of the last IL-2 dose will convert to management according to [Section 5.2.1.4](#), Table 4 and resulting AE grade and Treatment Discontinuation assignment forming the basis for DLT determination.
- Grade 5 toxicity

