5.2.1.2 Rules for Dose Escalation

Dose-limiting toxicities (DLT's) observed in course 1 will be used to determine escalation to the next dose level. A course is 12 weeks. The study will use a 3 + 3 trial design for IL-2 dose escalation. The first 3 patients will be enrolled at Dose Level 1. If no dose-limiting toxicities (DLT's) occur in the first 3 patients over treatment course 1, Dose Level 2 will then open for enrollment of the next 3 patients. In the absence of DLT's in three patients treated at Dose Level 2, then Dose Level 3 will open for enrollment of the next 3 patients.

If 1 of 3 subjects in a cohort experiences a DLT, the Cohort will expand to 6 pts. If only 1 of 6 patients experiences a DLT with all patients followed for safety endpoints to the end of course 1, then the next cohort dose level will open to enroll.

If two or more patients in a cohort experience a DLT, that dose level exceeds the MTD.

If two or more delayed DLT's (i.e., DLT's that occur after course 1) are noted within a dose-escalation cohort, accrual will be held pending safety analysis by the Principal Investigator and Merck and restarted only with Principal Investigator and Sponsor approvals with IRB and FDA notification.

Dose escalations or de-escalations of pembrolizumab are not allowed. Treatment delays for toxicity are allowable as described in [Section 5.2.1.4](#). Patients enrolled into Dose Level 3 who require treatment interruption and meet restarting criteria as described in [Section 5.2.1.4](#) may have IL-2 dosing de-escalated to the IV IL-2 Dose Level 2 for the subsequent treatment cycle and/or course(s) 2 and/or 3. Individual patient IL-2 dosing cannot be escalated.

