Subjects should be assessed for possible ECIs prior to each dose. Lab results should be evaluated and subjects should be asked for signs and symptoms suggestive of an immune-related event. Subjects who develop an ECI thought to be immune-related should have additional testing to rule out other etiologic causes. If lab results or symptoms indicate a possible immune-related ECI, then additional testing should be performed to rule out other etiologic causes. If no other cause is found, then it is assumed to be immune-related.

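### The DLT definition requires that progression and intercurrent illness be clearly excluded, so on a literal reading events of uncertain cause go uncounted even when judged possibly or probably drug-related

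*Combined protocol and SAP*

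**What the plan says.** Section 5.2.1.3 sets three conditions in one sentence. The event must be "clearly not related to disease progression or intercurrent illness". It counts "if judged by the investigator to be possibly, probably, or definitely related to study treatments". And it must be one of those "that meet or exceed the following severity criteria". The bulleted criteria that follow, including the one for Grade 5 toxicity, all stand under this lead-in.

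Section 5.2.1.2 makes the resulting count decisive: "Dose-limiting toxicities (DLT's) observed in course 1 will be used to determine escalation to the next dose level". It continues: "If 1 of 3 subjects in a cohort experiences a DLT, the Cohort will expand to 6 pts", and "If two or more patients in a cohort experience a DLT, that dose level exceeds the MTD". One DLT in six opens the next level.

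Three other places touch on cause without deciding DLT status. Section 5.4.1 asks for attempts to rule out metastatic disease and infection when an immune-type event occurs. Section 7.3.3.2, on events of clinical interest, says: "If no other cause is found, then it is assumed to be immune-related". Table 7 in section 7.3.4 records causality as yes or no for the Merck product only. The three-step relatedness scale used in the DLT sentence is not defined anywhere.

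**The concern.** A rating of possibly related often means that another explanation is still open. If that explanation is the cancer or an infection, the event passes the relatedness test and fails the first test. The word *clearly* is attached to ruling the alternative cause out. In a safety count the more cautious arrangement attaches it to ruling the alternative cause in.

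Such events are foreseeable in this population. Table 2 admits patients with liver metastases and AST/ALT up to 5 times the upper limit of normal. Grade 3 or 4 liver test elevation leads to permanent discontinuation in Table 4, and that assignment feeds the DLT determination. Infection during IL-2 is anticipated in Tables 10 and 11. The DLT window is a 12-week course, long enough for progression and toxicity to overlap.

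At stake is the escalation decision. Leaving doubtful events out can only lower the count, and a lower count favours opening the next IL-2 level.

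**Working it through.** **Step 1: the wording.** Take an event that meets the severity criteria and set the two tests side by side.

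| Progression or intercurrent illness | Relation to study treatment | Literal section 5.2.1.3 | With the clause reversed |
|---|---|---|---|
| Clearly excluded | At least possible | Counts | Counts |
| Neither excluded nor established | At least possible | Does not count | Counts |
| Clearly the cause | Any | Does not count | Does not count |
| Any | Not related | Does not count | Does not count |

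Only the second row changes. No section assigns that row to either side.

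**Step 2: effect on one cohort.** Under section 5.2.1.2, dropping one patient's event changes the decision as follows:

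- 2 of 6 (exceeds the MTD) becomes 1 of 6 (next level opens).
- 1 of 3 (expand to 6) becomes 0 of 3 (next level opens).

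**Step 3: illustration of size.** The plan states no DLT rate, error rate or escalation probability, so there is no figure of its own to reproduce. The inputs are:

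- the 3+3 rule, from section 5.2.1.2;
- p, the true probability that a patient has a DLT (assumed);
- f, the share of patients with a true DLT who go uncounted because another cause is not clearly excluded (assumed, 10% to 40%).

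A level is cleared with 0 of 3, or with 1 of 3 followed by 0 of the next 3:

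P(clear) = (1−p)³ + 3p(1−p)² × (1−p)³ = (1−p)³ + 3p(1−p)⁵

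With uncounted events, p is replaced by p(1−f).

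For p = 0.33:

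- f = 0: 0.67³ + 3(0.33)(0.67⁵) = 0.301 + 0.134 = 0.434
- f = 0.10, effective rate 0.297: 0.347 + 0.153 = 0.500
- f = 0.25, effective rate 0.2475: 0.426 + 0.179 = 0.605
- f = 0.40, effective rate 0.198: 0.516 + 0.197 = 0.713

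For p = 0.40, the same formula gives 0.309 (f = 0), 0.378 (f = 0.10), 0.494 (f = 0.25) and 0.622 (f = 0.40).

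**The case against.** The best defence is that the sentence is badly phrased but harmless. It says that DLTs include such events, which is not strictly exhaustive, and an investigator may take the relatedness judgement as the operative test. The intent may well have been the ordinary rule. That is fair as to intent. It does not settle what the text says, and two investigators could classify the same event differently.

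Safeguards also exist. The work-up in section 5.4.1 targets the same kinds of rival cause and will resolve some doubtful events, although it is written for pembrolizumab events. The Safety Data Review Board in section 8.1.1 looks at all AEs and SAEs as well as DLTs before giving direction on escalation, so an uncounted severe event is still seen. Section 5.8 allows early termination on adverse reactions whether or not they are DLTs. These points soften the effect. They do not replace the fixed count in section 5.2.1.2 or say how an unresolved event enters it.

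Two stronger readings are tempting, and the documents do not support them.

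- A reader might infer that almost no event rated possibly related could ever count. The clause names only two rival causes. An event can be merely possible because of supportive drugs (Tables 11 and 12), other concomitant medication, or late effects of a permitted earlier checkpoint antibody, and still be clearly neither progression nor intercurrent illness.
- A reader might infer that section 7.3.3.2 sets the opposite default. It also asks for other causes to be ruled out first, and it presumes immune causation only when none is found. Such an event would normally meet section 5.2.1.3 too. The two differ only where a rival cause is neither found nor clearly excluded, and section 7.3.3.2 does not govern DLT classification.

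**Conclusion.** The point holds as a defect in the definition. Taken literally, the two tests leave out events of unresolved cause even when the investigator judges them possibly or probably drug-related, and no section supplies another rule. The direction of any error is towards clearing a level. That follows from the wording and the 3+3 rule and needs no assumed rate.

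The size cannot be known from the documents. The rise from 0.43 to between 0.50 and 0.71 at a true rate of 33% rests on an assumed rate and an assumed uncounted share. It further supposes that each uncounted event is truly drug-caused, that the investigator discards all of them, and that the patient has no second, unambiguous DLT, since the rule counts patients. At Dose Level 3, clearing a level means only that it is not declared above the MTD, because no higher level follows. The probabilities show how sensitive a cohort of 3 to 6 patients is to one event. They are not a forecast for this trial. The correction is worth making because it is cheap and the definition carries the escalation decision.

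**What to change.** Reword the lead-in sentence of section 5.2.1.3 so that *clearly* applies to establishing the alternative cause: DLTs are adverse experiences meeting the existing severity criteria that the investigator judges at least possibly related to study treatments, except those clearly due to disease progression or intercurrent illness. Events whose cause stays unresolved after work-up would then count.

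The cost is one sentence and a few more events counted as DLTs, so a cohort will sometimes expand or stop where it would otherwise have cleared. The severity criteria, doses and management rules are unchanged. If this is already the intended reading, the edit only makes the text say so.

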5.2.1.4 Dose Modification

Adverse events (both non-serious and serious) associated with pembrolizumab exposure may represent an immunologic etiology. These adverse events may occur shortly after the first dose or several months after the last dose of treatment. Pembrolizumab must be withheld for drug-related toxicities and severe or life-threatening AEs as per Table 4 below. See [Section 5.4.1](#) and Events of Clinical Interest Guidance Document for supportive care guidelines, including use of corticosteroids.

Dose escalations or de-escalations of pembrolizumab are not allowed.

SQ IL-2 must be withheld for drug-related toxicities and severe or life-threatening AEs as per Table 4 below. SQ IL-2 associated with AE's requiring treatment interruption can be restarted at a reduced dose not lower than a 50% reduction of the recommended 125,000 U/kg dose.

If possible, the Investigator may attribute each toxicity event to pembrolizumab or IL-2 alone with a resulting dose modification applied to a single study drug. For example, local IL-2 injection site reaction could result in a hold of SQ IL-2 dosing with pembrolizumab continued without interruption.

Patients enrolled into Dose Level 3 who require treatment interruption and meet restarting criteria as described in Table 4 may have IL-2 dosing de-escalated to Dose Level 2 for the subsequent treatment cycle or course(s). Individual patient IL-2 dosing cannot be escalated.

Table 4 Dose Modification Guidelines for Drug-Related Adverse Events

General instructions:				
Immune-related AEs	Toxicity grade or conditions (CTCAEv5.0)	Action taken to pembrolizumab	irAE management with corticosteroid and/or other therapies	Monitor and follow-up
Pneumonitis	Grade 2	Withhold	
 Administer corticosteroids (initial dose of 1-2 mg/kg prednisone or equivalent) followed by taper 	
 Monitor participants for signs and symptoms of pneumonitis Evaluate participants with suspected pneumonitis with radiographic imaging and initiate corticosteroid treatment
	Grade 3 or 4, or recurrent Grade 2	Permanently discontinue		

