Hypothyroidism	Grade 2-4	Continue	
 Initiate thyroid replacement hormones (eg, levothyroxine or liothyronine) per standard of care 	
 Monitor for signs and symptoms of thyroid disorders.
Nephritis and Renal dysfunction	Grade 2	Withhold	
 Administer corticosteroids (prednisone 1-2 mg/kg or equivalent) followed by taper. 	
 Monitor changes of renal function
	Grade 3 or 4	Permanently discontinue		
Neurological Toxicities	Grade 2	Withhold	
 Based on severity of AE administer corticosteroids 	
 Ensure adequate evaluation to confirm etiology and/or exclude other causes
	Grade 3 or 4	Permanently discontinue		
Myocarditis	Asymptomatic Troponin Elevation	Withhold	
 Consider corticosteroids 	
 Repeat and monitor troponin Consider Cardiology consultation for further diagnostic workup
	Grade 2	Permanently discontinue	
 Administer corticosteroids (prednisone 2 mg/kg or equivalent) 	
 Hospitalization Urgent cardiology consultation for evaluation and management Taper steroid over at least 1 month with close monitoring Repeat cardiac MRI post treatment
	Grade 3 or 4	Permanently discontinue	
 Immediate initiation of corticosteroids (prednisone 2 mg/kg or equivalent or 1 g IV bolus) Consider adding second immunosuppressive agent 	
 Hospitalization to intensive cardiac care unit Emergent cardiology consultation for evaluation and management Taper steroid over at least 1 month with close monitoring Repeat cardiac MRI post treatment

Exfoliative Dermatologic Conditions	Suspected SJS, TEN, or DRESS	Withhold	
 Based on severity of AE administer corticosteroids 	
 Ensure adequate evaluation to confirm etiology or exclude other causes
	Confirmed SJS, TEN, or DRESS	Permanently discontinue		
All other immune-related AEs	Intolerable/persistent Grade 2	Withhold	
 Based on type and severity of AE administer corticosteroids 	
 Ensure adequate evaluation to confirm etiology and/or exclude other causes
	Grade 3	Withhold or discontinue based on the type of event.		

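### On the visible rows of Table 4, a related Grade 4 SQ IL-2 event that is neither judged immune-related nor covered by an organ row is a DLT at Dose Level 1 only if it causes a delay of more than 21 days; IV IL-2 toxicities sent to Table 4 meet the same gap

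*Combined protocol and SAP*

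**What the plan says.** Section 5.2.1.3 counts a related adverse event in course 1 (12 weeks) as a DLT only if it meets one of four criteria. None is a general grade threshold.

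- **Guideline discontinuation.** "For patients at Dose Level 1, all AE's resulting in Guideline recommendation for Treatment Discontinuation will also constitute a DLT". The sentence before it ties the guideline to Table 4 in 5.2.1.4 and describes that table as covering immune-mediated pathology.
- **Delay, any level.** "A delay in the scheduled administration of either component of therapy of > 21 days for pembrolizumab or SQ or IV bolus IL-2".
- **IV bolus only (Dose Levels 2 and 3).** Toxicity that has not stabilised within 48 hours, "or that fail to show improvement within 72 hours of the last IL-2 dose", passes to Table 4. The grade and discontinuation assignment found there decide whether it is a DLT.
- **Death.** Grade 5 toxicity.

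For SQ IL-2, Section 5.2.1.4 states: "SQ IL-2 must be withheld for drug-related toxicities and severe or life-threatening AEs as per Table 4 below". The drug-action column of Table 4 is "Action taken to pembrolizumab", its first column is headed as immune-related events, and its last row is "All other immune-related AEs", with permanent discontinuation at Grade 4 or recurrent Grade 3. Section 5.2.1.4 also gives an example of an IL-2-only event: "local IL-2 injection site reaction could result in a hold of SQ IL-2 dosing with pembrolizumab continued without interruption".

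Under Section 5.2.1.2, if the first 3 patients have no DLT, "Dose Level 2 will then open for enrollment of the next 3 patients". One DLT in 3 expands the cohort to 6, and 1 in 6 opens the next level. Two or more mean that the level exceeds the MTD.

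**The concern.** Dose Level 1 is where the combination is first tested, and its DLT count decides whether patients go on to IV bolus IL-2. A DLT rule should capture a life-threatening event related to either drug. Here the severity route depends on a table written around immune-related events and pembrolizumab, while SQ IL-2 can also cause toxicity that is not immune-related. Section 5.2.1.4 lets SQ IL-2 restart after a hold at a dose as low as half of 125,000 U/kg. A patient could therefore have a related Grade 4 event, restart at a reduced dose within 21 days, and be counted as DLT-free. At stake is the primary objective, safety and tolerability, and the decision to open the next level.

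**Working it through.** The plan states no DLT rate or operating characteristic, so there is no figure to reproduce. The check is to run one event through each criterion.

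**Step 1. Dose Level 1.** Take related Grade 4 hypotension during SQ dosing, not fatal and not judged immune-related.

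| Criterion (5.2.1.3) | Does it apply? |
|---|---|
| Table 4 discontinuation | No. There is no hypotension row, and the catch-all is limited to immune-related events |
| 48/72-hour test | No. It is written for IV bolus IL-2 at Dose Levels 2 and 3 |
| Grade 5 | No. The event is not fatal |
| Delay of more than 21 days | Only if dosing is held that long |

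Table 5 adds no route, because it covers pembrolizumab infusion reactions. Section 13.4 is written for high-dose IL-2 and enters the DLT definition only through the IV bolus criterion. A severe injection site reaction gives the same result.

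**Step 2. The remaining route for SQ IL-2.** Dosing 5 days a week for 6 weeks, starting on day 1, puts doses on days 1-5, 8-12, ..., 36-40 (30 doses). The first day past the limit is the first withheld dose + 22. A hold from day 18 gives 18 + 22 = 40, the last planned dose. A hold from day 19 gives 41, after the last planned dose. From day 19 on (1 + 15 = 16 of the 30 doses), no planned SQ dose in course 1 lies beyond the limit, and the text does not say how such a hold is scored.

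**Step 3. Dose Levels 2 and 3.** Persistent IV IL-2 hypotension that fails the 48/72-hour test is sent to Table 4 for a discontinuation assignment. It finds the same rows, so on the visible text there is none to apply.

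**Step 4. Consequence for escalation.** No rate is needed for this. If one of the first 3 patients has an uncounted event and there is no other DLT, the next level opens after 3 patients instead of expanding to 6. If two do, the level passes although a count including them would put it above the MTD.

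**Step 5. Illustration on assumed rates.** Let p be the chance per patient of a counted DLT, with patients independent.

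P(level passes) = (1-p)^3 + 3p(1-p)^2 × (1-p)^3

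Expected patients = 3 + 3 × 3p(1-p)^2

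| p | P(pass) | Expected patients |
|---|---|---|
| 0.10 | 0.729 + 0.243 × 0.729 = 0.906 | 3 + 3 × 0.243 = 3.73 |
| 0.20 | 0.512 + 0.384 × 0.512 = 0.709 | 3 + 3 × 0.384 = 4.15 |
| 0.30 | 0.343 + 0.441 × 0.343 = 0.494 | 3 + 3 × 0.441 = 4.32 |
| 0.40 | 0.216 + 0.432 × 0.216 = 0.309 | 3 + 3 × 0.432 = 4.30 |

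Suppose 10% of patients have a DLT that counts now, and a further 10%, 20% or 30% have an event of the Step 1 kind that never causes a delay over 21 days. As written, the pass probability is 0.906 in all three cases. With those events counted, it is 0.709, 0.494 or 0.309. All of these rates are assumptions.

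**The case against.** The strongest reply is that Table 4 was meant to cover IL-2 toxicity generally. Its title speaks of drug-related events, 5.2.1.4 applies it to SQ IL-2, and 5.2.1.3 sends unresolved IV IL-2 toxicity to it. On that reading the catch-all row already makes any related Grade 4 event a DLT. In addition, the general-instructions cell is blank in the text supplied, and 5.2.1.4 refers to restarting criteria in Table 4 that are hardly visible there, so a general rule may have been lost in extraction. This much stands: intent is arguable, and the point is conditional on the visible rows and headings. It does not remove the problem, because the row labels limit the table to immune-related events, and a DLT rule should not depend on reading past its labels.

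Second, the gap is narrow. The liver, bowel, kidney, nerve and heart rows catch some IL-2 effects. A Grade 4 event judged immune-related is a DLT, and 7.3.3.2 presumes an immune cause for a possible immune-related event of clinical interest when no other is found. That also stands. A reader might infer that no non-fatal SQ IL-2 toxicity can be a DLT on severity; these provisions show otherwise. But where IL-2 itself is the evident cause, the presumption does not clearly apply.

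Third, the safety review board in 8.1.1 sees AEs and SAEs as well as DLTs. A reader might infer that escalation would go ahead regardless of a life-threatening event; the documents do not support that, since the board can intervene. Its judgement does not change the count, however, and 5.2.1.2 ties opening a level to the count.

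Finally, basing DLTs on discontinuation or delay rather than raw grade is a defensible choice for IL-2, and 4.2.3.2 expects SQ dosing to be much less toxic than high-dose IV. Both are fair, and both argue for a narrow fix.

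**Conclusion.** The point holds as a gap in scope, conditional on Table 4 as it can be read. At Dose Level 1, a related Grade 4 event that is not judged immune-related and fits no organ row is a DLT only through a delay of more than 21 days. IV IL-2 toxicities that reach Table 4 meet the same missing row, so it would be wrong to treat this as a Dose Level 1 problem alone.

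The direct consequence is certain in form: one uncounted event can avoid expansion, and two can pass a level that should stop. Its frequency is unknown. It would be tempting to read the fall in pass probability from 0.906 to 0.309 as the size of the error; the documents do not support that, because they give no event rate and the figure assumes that none of these events causes a long delay. This is a clarification worth making for patient safety. It does not show that the escalation design is unsound.

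**What to change.** Add to Section 5.2.1.3:

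*For DLT determination, the Table 4 row "All other immune-related AEs" applies to any related adverse event with no other Table 4 row, whether or not immune-related. Grade 4 or recurrent Grade 3 is a DLT, except laboratory changes that are asymptomatic and need no intervention. At Dose Levels 2 and 3 this applies only after the 48/72-hour test is failed.*

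This uses the thresholds already in the table, closes the gap at all three levels, and leaves expected acute IV IL-2 toxicity under the existing test. If the complete Table 4 already contains such a rule in its general instructions, a cross-reference from 5.2.1.3 is enough. The 21-day limit can stay as it is, and I would not add a separate recovery-time rule for Grade 3 events.

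No visit or data item is added. The real cost is that Dose Level 1 may expand to 6 patients more often or be declared above the MTD, and Table 1 offers no lower level to fall back to. At assumed total DLT rates of 10%, 20% or 30%, the expected cohort is 3.73, 4.15 or 4.32 patients against 3 with no DLTs, and the chance of exceeding the MTD is 1 - 0.906 = 9%, 1 - 0.709 = 29% or 1 - 0.494 = 51%. The true cost is unknown for want of an event rate.
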